12.3. Analysis Sets

12.3.1. Intention to Treat (ITT) Population

The intention-to-treat (ITT) population includes all participants randomized according to their initial randomized assignment regardless of the treatment actually received.

12.3.2. Antiviral Efficacy Analysis Population

The antiviral efficacy analysis population will consist of all randomized participants with a baseline viral load $>10^5$ copies/mL.

12.3.3. Per Protocol (PP) Population

The per-protocol (PP) population includes all ITT participants who did not have any major protocol deviations. The final determination of the exclusion of subjects from the PP population will be made prior to the database lock.

12.3.4. Safety Population

The safety population will include all randomized subjects who received at least one dose of the study drug.

12.4. Statistical Analyses

12.4.1. General Considerations

This is a double-blind placebo controlled randomized trial testing the superiority of LAM-002A compared to placebo for Day 4 viral load at the two-sided overall type I error rate of 0.20. Secondary hypotheses will be described according to the appropriate summary statistics (e.g., proportions for categorical data, means with 95% confidence intervals for continuous data, median for time-to-event data). Diagnostic tests and sensitivity analyses will be performed. Parametric distributional assumptions will be checked. If assumptions fail, other distributions will be considered prior to transformations and non-parametric methods for sensitivity analysis. A statistical analysis plan (SAP) will be developed and filed with the study sponsor prior to database lock.

12.4.2. Comparability of Baseline Characteristics.

Distributions of baseline demographic and clinical characteristics will be summarized by intervention group. Comparability for continuous variables will be examined graphically and by summary statistics (means, medians, quartiles, etc.). Categorical variables will be examined by calculating frequency distributions. No inferential statistics will be calculated.

12.4.3. Analysis of Primary Outcome: Viral Load in Nasopharyngeal Samples at Day 4

The primary analysis will test whether the viral load in nasopharyngeal samples is lower at Day 4 in those receiving LAM-002A compared to placebo. All participants in the antiviral efficacy analysis set (i.e. the subgroup with baseline viral load >10⁵ copies/mL) will be included in the primary analysis. Viral load will be measured by a qRT-PCR test at Days 1 and 4. The analysis for the primary endpoint will focus on the log₁₀ viral RNA on Day 4. A repeated measures mixed model will be used to compare the two treatment groups. The mixed model will jointly model day 1 and day 4 viral load and will allow for the inclusion of all participants with at least one viral load assessment [Carpenter 2007]. The model will include fixed effects for treatment and age. Random effects will be included for subject and site. Linear contrasts will be used to compare the difference between groups for Day 4. This difference will be conditional on baseline viral load and is equivalent to an analysis adjusted for baseline [Carpenter 2007]. 95% CIs will be estimated for treatment differences at Day 4. A supportive analysis will be conducted using the ITT population, stratified by baseline viral load >10⁵ copies/mL vs. viral load ≤10⁵ copies/mL.

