11. EFFICACY ASSESSMENTS

11.1. Primary Efficacy Endpoint: Viral Clearance at Day 4

The primary efficacy outcome measure evaluates SARS-CoV-2 viral load at Day 4 for LAM-002A or placebo-treated subjects. SARS-CoV-2 viral load will be measured in nasopharyngeal specimens by a qRT-PCR method. Analysis will focus on log_{10} viral load on Day 4 adjusted for baseline viral load at Day 1 in subjects with baseline viral load >10⁵ copies/mL.

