12. STATISTICAL CONSIDERATIONS

This is a double-blind placebo-controlled trial to determine the superiority of LAM-002A compared to placebo in reducing viral load during a 10-day course of therapy.

COVID-19 patients that fulfill all enrollment criteria and provide informed consent to study participation will have their baseline assessments performed and will be randomized using a permuted block scheme (with variable block size) in a 1:1 ratio to one of the two groups: (1) LAM-002A, or (2) placebo.

The study will include an early evaluation of safety, and an interim analysis. Full details of the statistical methods will be developed and outlined in the statistical analysis plan (SAP) and filed with the study sponsor prior to database lock.

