12.2. Sample Size Determination

The study is designed to have high power at a moderate significance level to detect a signal of benefit for the viral load outcome. The sample size calculation is based on the primary endpoint of interest: log₁₀ respiratory (nasopharyngeal swab) viral load at Day 4 post-randomization.

Given the limited data on the variability of the change in log_{10} viral load, the study is powered based on detecting a moderate standardized effect size of 0.3 using an analysis of covariance (ANCOVA), adjusting for baseline log_{10} viral load. (NOTE: For ANCOVA, the effect size is the standard deviation of the treatment means divided by the pooled standard deviations of the observations. An ANCOVA standardized effect size of 0.3 is equivalent to a Cohen's d of 0.60). To be conservative, a R-squared of 0 between the log_{10} viral RNA at 4-days and baseline log_{10} viral RNA was assumed. With a power of 90%, and a type I error rate of 20% (2-sided), it will be possible to detect the hypothesized 0.3 standardized effect size with 74 total patients – 37 patients per group with a 1:1 randomization. We will enroll a sample size of 142 to assure that a sufficient number of participants with baseline viral load >10⁵ copies/ml. The table below shows the power to detect an effect size of 0.3 given 10% loss to follow-up and various proportions enrolled with baseline viral load >10⁵ copies ml.

	Proportion of Enrolled Participants with >10⁵ copies/ml						
	0.40	0.50	0.60	0.70	0.80	0.90	1.00
Power to Detect Effect Size of 0.3	0.79	0.86	0.91	0.94	0.96	0.97	0.98

Based on available data regarding the distribution of viral load, it is conservatively estimated that \geq 50% of randomized participants will have a baseline viral load $>10^5$ copies/mL. The table above demonstrates that enrolling 142 will provide sufficient power even if the proportion with baseline viral load $>10^5$ copies/ml is as low as 40%. The prevalence of this subgroup will be monitored and adjustments to overall sample size may be made if necessary.

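### The terms listed for the primary mixed model in Section 12.4.3 do not yield the baseline-adjusted Day 4 comparison that the section promises

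*Combined protocol and SAP*

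**What the plan says.** Section 12.4.3 describes a repeated measures mixed model with Day 1 and Day 4 log10 viral load as joint responses. The terms are: "The model will include fixed effects for treatment and age. Random effects will be included for subject and site". It then says: "Linear contrasts will be used to compare the difference between groups for Day 4". Of that contrast it claims: "This difference will be conditional on baseline viral load and is equivalent to an analysis adjusted for baseline", and cites a practical guide to missing data in randomised trials.

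Other sections bear on the point:
- Section 12.3.2: the primary population "will consist of all randomized participants with a baseline viral load" above 10^5 copies/mL, so it is selected on one of the two modelled responses.
- Section 12.4.1: superiority is tested "for Day 4 viral load at the two-sided overall type I error rate of 0.20".
- Section 12.2: the trial is sized "using an analysis of covariance (ANCOVA), adjusting for baseline" log10 viral load.
- Section 11.1: Day 4 is to be "adjusted for baseline viral load at Day 1 in subjects with baseline viral load" above the same cut.
- Section 12.4.6: this is the only place in Section 12 where a time term appears, and there it is crossed with the subgroup variable, not with treatment.
- Section 12: "Full details of the statistical methods will be developed and outlined in the statistical analysis plan (SAP"), to be filed before database lock. The document supplied contains no text of that plan.

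**The concern.** This is the trial's single primary test, and the listed terms do not define it. Three things are missing.

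- **Day 4 contrast.** With treatment as the only treatment-related term, the model has one treatment coefficient shared by a predose day and Day 4.
- **Baseline adjustment.** The claimed equivalence needs one of three things: baseline as a covariate, Day 1 means constrained equal across arms, or a contrast conditional on baseline computed from an unstructured covariance. None is stated.
- **Variances.** A random subject effect with a common residual makes the Day 1 and Day 4 variances equal. Truncating Day 1 at 10^5 makes them unequal.

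An analyst who fills these gaps in the most obvious way could forgo the precision from baseline adjustment, or use a standard error that is too small.

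**Working it through.** **Inputs from the protocol.** Section 12.2 gives two-sided alpha 0.20, power 0.90, d = 0.60, R-squared 0, 37 per arm, 142 enrolled and 10% loss. Section 10.1 gives an LLOQ of 3.348 log10 copies/mL. The Day 1 to Day 4 correlation, the SDs, the placebo decline and a numerical value for results below the LLOQ are not given, so they are assumed below.

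**1. The plan's own figures.** A two-sample calculation with d = 0.60 and alpha 0.20 gives 37 per arm and power 0.90. At 50% prevalence, 142 × 0.9 × 0.5 / 2 = 32 per arm gives 0.865 (stated 0.86). At 80%, 51 per arm gives 0.959 (stated 0.96). All seven table entries reproduce within two points.

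**2. The listed terms.** Day 1 is predose, so its expected treatment difference is 0. With complete data the single coefficient estimates (0 + 0.60)/2 = 0.30 SD.

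**3. Ways of completing the model.** Simulation with 37 per arm, a true Day 4 difference of 0.60, SD 1 on both days, a placebo fall of 1.5, correlations 0 to 0.7 and 1,000 trials per scenario (site and missing data left out):

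| Model | Mean estimate (absolute) | Power |
|---|---|---|
| As listed | 0.30 | 0.52-0.53 |
| Day added | 0.30 | 0.55-0.69 |
| Day and treatment-by-day, Day 1 means free | 0.60 | 0.89-0.91 |
| Same, Day 1 means equal | 0.59-0.60 | 0.91-0.99 |
| ANCOVA on baseline | 0.59-0.61 | 0.90-0.99 |

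With free Day 1 means the SD of the estimate stays at 0.23-0.25 whatever the correlation: it is the raw Day 4 difference. With equal Day 1 means, or with ANCOVA, it falls from 0.24 at correlation 0 to 0.16 at 0.7.

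Free means can still give the adjusted contrast if it is computed as (Day 4 difference) − b × (Day 1 difference), with b = Cov(Day 1, Day 4)/Var(Day 1) from an unstructured covariance. On one simulated data set with 32 per arm this was −0.58565, identical to ANCOVA; the raw difference was −0.59944.

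At 32 per arm, the raw contrast has power 0.865 at any correlation. ANCOVA, using d/√(1−ρ²), has 0.86, 0.89, 0.93 and 0.98 at ρ = 0, 0.3, 0.5 and 0.7, where ρ is the correlation within the analysed subgroup.

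**4. Equal variances after truncation.** Assume a normal baseline and equal variances before selection.
- 50% above the cut: Day 1 variance becomes 1 − 2/π = 0.363. At pre-selection correlation 0.3, Day 4 variance is 1 − 0.09 × 0.637 = 0.943. The SD ratio r is √(0.943/0.363) = 1.61.
- 80% above the cut: Day 1 variance is 0.583. At correlation 0.7, Day 4 variance is 1 − 0.49 × 0.417 = 0.796, so r = 1.17.

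An equal-variance fit with free means estimates the Day 4 variance by the average of the two. Its type I error is therefore 2(1 − Φ(1.2816 √((1 + r²)/(2r²)))): 0.233 at r = 1.17 and 0.286 at r = 1.61.

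Simulation at 32 per arm gave 0.23-0.28 with free Day 1 means and 0.24-0.29 with a common Day 1 mean, so the constraint alone does not cure it. Direct REML fits at three settings gave 0.234-0.284 for the equal-variance model with a common Day 1 mean and 0.191-0.204 for the unstructured one (Monte Carlo SE about 0.009).

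**5. With an assay floor** at 3.348 and an assumed baseline SD of 1.5-2.0 log10, equal-variance fit:
- Half the LLOQ substituted: 0.23-0.27 for a 1 log10 decline, 0.21-0.23 for 2 log10.
- The LLOQ substituted: 0.22-0.25 for 1 log10, 0.19-0.22 for 2 log10.

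Across steps 4 and 5 ANCOVA stayed at 0.19-0.21, and the common Day 1 mean with unstructured covariance at 0.20-0.21 in the main simulations. The floor cases were not checked by direct REML. Age, site and missing Day 4 values were not part of the type I error simulations.

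**The case against.** The strongest reply is that the target is not in doubt. Section 12.4.3 asks for a Day 4 contrast with a confidence interval at Day 4, and Sections 11.1 and 12.2 say adjusted for baseline. The term list in Section 12.4.6 mentions time but omits age, which suggests that these lists are abbreviated. The equivalence claim is referenced to an outside source that may define the constraint or covariance and that cannot be seen here. Full details are deferred to the SAP, and Section 12.4.1 promises checks of parametric assumptions.

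Most of this stands, and it rules out several stronger readings.
- A reader might infer that the trial would report half the effect with power near 0.5. The documents do not support that: a single coefficient is not a Day 4 contrast, so nobody following the whole paragraph could report it.
- A reader might infer that equal Day 1 means are required. They are one of three routes.
- A reader might say that no covariance is stated. A random subject effect does imply one, with equal variances; what is absent is any allowance for unequal variances.
- A reader might infer that type I error will exceed 0.20. That needs an equal-variance fit and a set of assumptions absent from the documents, and in one floor scenario there was essentially no excess.

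What the reply does not remove is that the protocol says what the model will include, the list does not define the primary test, and the reasonable completions are different estimators with different error rates.

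**Conclusion.** The point holds as an incomplete and partly inconsistent specification of the primary analysis, worth correcting before lock. It is not evidence that a wrong model would be run.

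The absence of day and treatment-by-day terms, and of any stated route to baseline adjustment, is certain from the text. The halved coefficient (0.30 for 0.60 SD) shows that the list is incomplete and does not predict the result. With the obvious terms added and free Day 1 means, the cost is the forgone gain from adjustment: at 32 per arm, 0.865 against 0.89-0.98 for within-subgroup correlations of 0.3-0.7. Because Section 12.2 assumes R-squared 0, there is no loss against the stated power if the intent is carried out.

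The type I error of about 0.23-0.29 is conditional on an equal-variance fit, a normal baseline, 50-80% prevalence, pre-selection correlation 0.3-0.7 and no floor. With a floor it ranges from 0.27 down to no excess. The two sets of correlations are on different scales: 0.3-0.7 before selection is about 0.19-0.60 within the subgroup (0.3/1.61 and 0.7/1.17).

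**What to change.** Amend Section 12.4.3, or settle it in the SAP before lock, in one of two ways.

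- **(a)** Use the ANCOVA on which Section 12.2 is sized: Day 4 log10 viral load on treatment, baseline log10 viral load and age, with site as a random effect. The small downside is that participants without a Day 4 value contribute nothing directly.
- **(b)** Keep the joint model with fixed effects for day, treatment-by-day and age, Day 1 means constrained equal across arms, and site random. Use an unstructured 2×2 within-subject covariance that replaces the random subject effect, since the two together are not identifiable. Name the treatment difference at Day 4 as the test.

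Either takes one or two sentences and needs no new data or participants.

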6.1. Inclusion Criteria

Study candidates must meet all of the following inclusion criteria to be eligible for participation in this study:

- 1. Men and women of age ≥ 18 years.
- 2. Written documentation of SARS-CoV-2 infection confirmed by a validated test.
- Presence of ≥1 of the following COVID 19-related symptoms indicating mild disease: fever (temperature ≥100.4), anosmia (loss of taste or smell), cough, sore throat, gastrointestinal complaints (e.g. nausea, vomiting or diarrhea), chills, congestion or runny nose, headaches, muscle or body aches, fatigue, or asymptomatic patients who have tested positive for COVID-19 via a validated test within the past 4 days.
- 4. If symptomatic, symptom onset ≤ 8 days.
- 5. For female subjects of childbearing potential, a negative urine (or serum) pregnancy test.
- 6. For female subjects of childbearing potential, willingness to use a protocol-recommended method of contraception from the start of the screening period until \geq 30 days after the final dose of study therapy. *Note: A female subject is considered to be of childbearing potential unless she has had a hysterectomy, bilateral tubal ligation, or bilateral oophorectomy; has medically documented ovarian failure (with serum estradiol and follicle-stimulating hormone [FSH] levels within the institutional laboratory postmenopausal range and a negative serum or urine beta human chorionic gonadotropin [\betaHCG]); or is menopausal (age \geq50 years with amenorrhea for \geq6 months).*
- 7. For male subjects who can father a child and are having intercourse with females of childbearing potential who are not using adequate contraception, willingness to use a protocol-recommended method of contraception from the start of study therapy until ≥30 days after the final dose of study therapy and to refrain from sperm donation from the start of study therapy until ≥90 days after administration of the final dose of study therapy. Note: A male subject is considered able to father a child unless he has had a bilateral vasectomy with documented aspermia or a bilateral orchiectomy.
- 8. Willingness and ability of the subject to ingest study drug capsules.
- 9. Willingness of the subject to comply with scheduled visits, drug administration plan, protocol-specified laboratory tests, study procedures, and study restrictions.

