12.4.6. Subgroup Analyses

Heterogeneity of treatment effect (HTE) for the primary and secondary progression to hospitalization or death outcome will be examined for the following subgroup variables: days from onset of symptoms to randomization, NEWS score at randomization and sex (male vs. female). HTE will be evaluated within a mixed model for the primary outcome and a logistic regression for the secondary progression outcome. The models will include treatment, site, the subgroup variable, and the interaction of the subgroup variable with time. Differences in means or risk with 95% confidence intervals will be estimated for the treatment difference within each level of the subgroup variable. The significance test of the interaction will be used to formally test HTE at the two-sided 0.05 significance level.

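### The primary Day 4 viral-load model leaves out days from symptom onset, a baseline variable the trial already needs; adding it could improve precision, by an amount the documents do not let us fix

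*Combined protocol and SAP*

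**What the plan says.** Section 12.4.3 sets out a repeated-measures mixed model for Day 1 and Day 4 log10 viral load in participants with baseline load above 10^5 copies/mL. On covariates it says "The model will include fixed effects for treatment and age". Subject and site are random, and the Day 4 contrast is conditional on baseline load. No other covariate is named.

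Symptom timing appears elsewhere:

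- **Section 6.1, criterion 4** begins "If symptomatic, symptom onset" and sets a limit of 8 days. Criterion 3 also admits asymptomatic people with a positive test in the previous 4 days.
- **Table 1, footnote f** has COVID-19 history recorded at screening.
- **Section 12.4.6** names "days from onset of symptoms to randomization" as one of three subgroup variables for the primary outcome, with NEWS score and sex.

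Sections 5.1, 7.1 and 12 describe 1:1 permuted-block randomisation and no strata. The synopsis and section 5.3 say that baseline viral-load results are not available before treatment starts. Membership of the primary analysis set is therefore unknown at allocation.

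**The concern.** Entry ranges from the day of onset to 8 days later, or occurs without symptoms. A single Day 1 value does not show whether load is still rising or already falling, so time since onset could carry information about Day 4 load that baseline load does not. If it does, leaving it out makes the standard error larger than it need be and lets a chance difference in onset between arms pass into the estimate.

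Permuted blocks balance arm sizes overall. They do not balance onset within a subgroup identified only later. At the plan's planning share of 50%, that subgroup has about 64 evaluable participants, where the plan's own table gives power of 0.86 against a 90% target. A baseline variable needing no new data collection is worth considering there.

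**Working it through.** **Inputs (section 12.2).** Power is 90% and alpha 0.20 two-sided. On effect size the plan says "An ANCOVA standardized effect size of 0.3 is equivalent to a Cohen's d of 0.60". On baseline load it says "To be conservative, a R-squared of 0 between" baseline and Day 4 values was assumed. The requirement is "37 patients per group with a 1:1 randomization", 74 in all. On enrolment: "We will enroll a sample size of 142". Loss to follow-up is 10%, and at least 50% are expected above 10^5 copies/mL.

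**Reproducing the plan.** n per arm = 2(1.2816 + 1.2816)² / 0.60² = 36.5, rounded up to 37, so 74 in total. A noncentral F calculation at N = 74 gives power 0.9005. For the table, N = 142 × 0.9 × share. Computed power for shares 0.4 to 1.0 is 0.801, 0.865, 0.908, 0.939, 0.959, 0.973 and 0.982. The plan states 0.79, 0.86, 0.91, 0.94, 0.96, 0.97 and 0.98. Agreement is within about 0.01, so the sample-size work stands.

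**Adding onset.** Let R² be the share of the remaining variance explained by onset after baseline load and age. The documents give no value, so 0 to 0.20 is an assumption. Noncentrality is N × 0.60² / [4(1 − R²)], with 1 and N − 2 − c degrees of freedom. Here c is 2 before the change (baseline load, age) and 4 after it (plus days from onset and an asymptomatic indicator).

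- Share 0.5: 142 × 0.9 × 0.5 = 63.9, about 64 evaluable.
- Share 0.4: 142 × 0.9 × 0.4 = 51.1, about 51 evaluable.
- Share 1.0: 142 × 0.9 = 127.8, about 128 evaluable.

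| Assumed R² | SE multiplier √(1 − R²) | Total N for 90% power | Power, 64 | Power, 51 | Power, 128 |
|---|---|---|---|---|---|
| 0 | 1.000 | 74 | 0.865 | 0.800 | 0.982 |
| 0.05 | 0.975 | 70 | 0.878 | 0.815 | 0.986 |
| 0.10 | 0.949 | 66 | 0.891 | 0.831 | 0.989 |
| 0.15 | 0.922 | 64 | 0.904 | 0.847 | 0.991 |
| 0.20 | 0.894 | 60 | 0.917 | 0.863 | 0.994 |

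At 64 evaluable, R² = 0.02 gives 0.870, and power reaches 0.90 at R² of about 0.15.

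**Cost of the two terms.** At R² = 0 the lost degrees of freedom reduce power by about 0.0002 at 64. Chance correlation of two covariates with treatment also inflates the variance by roughly 2/64 = 3%, which the table ignores. Break-even is therefore an R² near 3%.

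**If baseline load is itself prognostic.** The table keeps the plan's R² of 0 for baseline load. If baseline load explained 30% (an assumption), power at 64 would already be 0.941, and a further 5 to 10% from onset would add about 0.01 to 0.02.

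**Chance imbalance.** With equal arms, the standardised difference in mean onset has SD 2/√64 = 0.25. The chance that it exceeds 0.25 SD in either direction is about 32%. At R² = 0.10, a 0.25 SD imbalance moves the unadjusted estimate by 0.25 × √0.10 = 0.08 SD, against a design effect of 0.60. This is the same precision gain seen from another side, not an additional one. It applies to participants who have an onset date.

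**The case against.** The strongest reply is that this is a preference. No section says that onset predicts Day 4 load once baseline load is known, and section 12.2 concedes that data on variability are limited. Being a subgroup variable does not make onset prognostic, and the same argument would admit NEWS and sex. Section 12.4.6 already plans a mixed model of the primary outcome containing the subgroup variable. The 50% share is described as conservative, the sample size may be raised, and section 5.1 speaks of 142 participants with high baseline load. That would give about 128 evaluable and a gain of only 0.004 to 0.012. Full methods are deferred to a SAP to be filed before the database is locked.

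Most of this stands, and it limits the size of the point. It does not remove it. The section 12.4.6 model is separate from the primary estimate and, as written, crosses the subgroup variable with time, not treatment. Deferral to the SAP means there is still an opportunity to add the term; the primary model as stated does not contain it. Onset has a better claim than NEWS or sex because section 5.3 builds the design on treating early in infection.

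A reader might infer that the primary estimate is biased, that the trial is undersized, or that the plan contradicts itself by calling onset important and then ignoring it. The documents support none of these. Randomisation keeps the contrast valid without onset, the 74 reproduces, and the plan nowhere calls onset prognostic.

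**Conclusion.** The point holds as an optional improvement. The primary model omits a baseline variable that the trial must already hold for its symptomatic participants and that allocation does not balance within the analysed subgroup. The possible benefit at 64 evaluable is between nothing and about 5 percentage points of power (0.865 to 0.917), and at 51 evaluable up to about 6 (0.80 to 0.86). These figures rest on an assumed incremental R² of 0 to 20%, the 50% and 40% shares, 10% loss, and the plan's zero R² for baseline load. A prognostic baseline load or a larger qualifying share reduces the gain. So would a large asymptomatic fraction, since those participants contribute no onset time; their share is not stated. Adjustment accounts for a chance imbalance in onset; it does not prevent one, and there is no bias for it to correct.

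**What to change.** Before unblinding, state in section 12.4.3 and in the SAP that the primary model includes days from symptom onset as a fixed effect acting on the Day 4 response. In the joint Day 1 and Day 4 model the term must be allowed to differ by visit, because one effect common to both days would not let onset influence the change. Add an indicator for participants asymptomatic at entry, with their onset value set to a constant, so that none drop out for lack of a date. Use the same coding in section 12.4.6, which needs a rule for these participants and gives none.

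The cost is a few lines of text, the coding rule and two degrees of freedom on the Day 4 response. The gain may be negligible, or slightly negative below an R² of about 3%, if onset adds little beyond baseline load. No new data are needed and the planned sample size is unchanged. Added after unblinding, the same adjustment would look data-driven.
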